## SUMMARY

**Rationale:** Approximately 20% of the patients with acute ischemic stroke due to an intracranial large vessel occlusion (LVO) has a high-grade stenosis in the ipsilateral cervical carotid artery. It is uncertain whether immediate carotid artery stenting (CAS) of a cervical carotid artery stenosis during endovascular thrombectomy (EVT) is beneficial. Immediate CAS could improve cerebral perfusion and prevent recurrent ischemic stroke but could also increase the chance of intracranial hemorrhagic complications due to hyperperfusion syndrome or to the required antiplatelet treatment to prevent stent occlusion. Moreover, some patients end up with a severe disabling stroke after EVT. In these patients carotid revascularization by carotid endarterectomy (CEA) or CAS would usually not be performed but these patients would be treated by medical management only.

**Objective:** to assess the safety and efficacy of immediate cervical CAS during EVT in patients with acute ischemic stroke due to LVO with a high-grade stenosis >50% or occlusion of the ipsilateral cervical carotid artery.

**Study design:** prospective randomized open label controlled trial comparing immediate CAS during EVT versus EVT with deferred treatment of the cervical carotid artery lesion (deferred CAS/CEA or medical management alone). Outcome assessment will be blinded for treatment allocation.

**Study population:** patients with acute ischemic stroke with a CT-angiography proven intracranial LVO in the anterior circulation (ICA, A1, M1 or M2) as well as an ipsilateral cervical carotid artery tandem lesion of presumed atherosclerotic origin with a stenosis >50% or an ipsilateral acute proximal internal carotid artery occlusion who are treated with EVT according to the guidelines.

**Intervention (if applicable):** in the intervention group, the cervical carotid artery lesion will be treated with a stent during the EVT (just before or directly after intracranial thrombus removal), the control group will be treated according to the national guidelines with carotid endarterectomy of carotid artery stenting (for patients with non-disabling stroke) or medical management alone (for patients with severe disabling stroke).

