### **3. STUDY DESIGN**

This study is a phase 3 international multicenter randomized clinical trial with open label treatment and blinded outcome assessment (PROBE design). The study will be performed among thrombectomy capable stroke centers in the Netherlands and Belgium.

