## 8. METHODS

### 8.1 Study parameters/endpoints

#### 8.1.1 Main study parameter/endpoint

The primary outcome is the modified Rankin Scale Score at 90 days after stroke onset. The mRS is a disability scale ranging from 0 (no symptoms at all) to 6 (death). The mRS score will be assessed by a stroke research personnel by telephone interview, blinded for the treatment allocation.

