#### 8.1.2 Secondary study parameters/endpoints (if applicable)

Secondary endpoints are:

- mRS score of 0-1 at 90 days
- mRS score of 0-2 at 90 days
- mRS score of 0-3 at 90 days
- NIHSS score at 24 hours and day 5-7, or at discharge
- adequate recanalization after EVT (TICI 2b or higher)
- final infarct volume on brain CT at 24 hours
- arterial occlusive lesion (AOL) score on CTA at 24 hours
- any stroke within 90 days
- recurrent ipsilateral TIA/ischemic stroke within 90 days
- Carotid artery re-occlusion at 24 hours and 90 days.
- Mortality at 90 days
- Quality of life (EQ5D-5L) questionnaire at 90 days

For the purpose of health economic evaluation, additional questionnaires will be sent to the study participants at 90 days for measuring loss of productivity (IMTA productivity cost questionnaire (iPCQ)) and medical consumption (IMTA medical consumption questionnaire (iMCQ)).

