#### **8.2 Randomization, blinding and treatment allocation**

The randomization will be performed by a computer and web-based procedure, using permuted blocks. Back-up by telephone will be provided. Randomization is allowed when the CTA at baseline demonstrates an ipsilateral high-grade stenosis (>50%) or occlusion of the proximal ICA of presumed atherosclerotic origin. Although DSA is more reliable to distinguish carotid pseudo-occlusions from cervical atherosclerotic lesions in the ICA, randomization during the EVT can be very challenging and might lead to lower inclusion rates. And CTA has been shown to have acceptable diagnostic accuracy for true cervical ICA lesions. Only in case of significant doubt by the interventionist if there is a true cervical atherosclerotic lesion in the carotid artery, randomization is also allowed after the first angiographic run of the carotid artery that confirms the cervical atherosclerotic lesion. Randomization will be stratified for center. Both the patient and treating physicians are aware of the treatment assignment. The 90 days follow up will be performed by certified research personnel blinded for the treatment allocation. The assessment of secondary endpoints will not be blinded as for several secondary endpoints it will be obvious whether the patient was treated with CAS or not. Information on treatment allocation will be kept separate from the main study database. An independent trial statistician will combine the data on treatment allocation with the clinical data in order to report to the data safety monitoring board (DSMB). The trial steering committee will be kept unaware of the exact results of the interim analyses on efficacy and safety. Only the recommendation to continue, modify or stop the trial will be communicated.

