### **HOW**

#### 24 hours NCCT:

1. The NCCT study should contain both thick (5mm) and thin slices (maximum of 2.5mm).
2. The NCCT study should include the whole head.

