## 19. GOVERNANCE OF THE CASES TRIAL

The steering committee of the trial will include 2 local principal investigators (one stroke neurologist and one neuro-interventionist) per participating center in Belgium and the Netherlands. The steering committee will meet twice a year and will discuss protocol changes, progress, publication and reporting of the trial. The steering committee is chaired by the prof.dr. [name], the national coordinator of Belgium and/or dr. [name], national coordinator in the Netherlands. The executive committee consists of coordinating neurologists, radiologists and vascular surgeons (see project team) and the coordinating project managers. They will meet every two weeks during the recruitment phase of the trial to discuss the progress of the trial. The executive committee will prepare the main publication and distribute the trial results among the steering committee. A trial advisory board will be installed, with 4 independent neurologists/neuro-interventionists and 3 patient representatives (two from Belgium (Flemish and French speaking) and one from the Netherlands). For all the CONTRAST trials there is an independent outcome assessment committee, imaging assessment committee and adverse event committee. These committees will report to the executive committee of the CASES trial. Within the CONTRAST consortium, the progress of all trials is being monitored by the scientific committee of CONTRAST. The overall performance of the CONTRAST consortium is evaluated by a board of governors.

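### Section 8.2 leaves the secondary endpoints unblinded for a reason that does not apply to infarct volume or to stroke and TIA adjudication

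*Protocol*

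**What the plan says.** The Summary states, without exception, "Outcome assessment will be blinded for treatment allocation". Section 3 describes the trial as having "open label treatment and blinded outcome assessment (PROBE design".

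For the primary endpoint, section 8.1.1 says "The mRS score will be assessed by a stroke research personnel by telephone interview, blinded for the treatment allocation". Section 8.2 repeats this more broadly: "The 90 days follow up will be performed by certified research personnel blinded for the treatment allocation". The next sentence of 8.2 then says of the secondary endpoints: "The assessment of secondary endpoints will not be blinded as for several secondary endpoints it will be obvious" whether CAS was performed.

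Section 8.1.2 lists twelve secondary endpoints. Among them are three dichotomies of the 90-day mRS (the first is "mRS score of 0-1 at 90 days"), infarct volume on 24-hour brain CT, any stroke, recurrent ipsilateral TIA or ischaemic stroke, and carotid re-occlusion. Haemorrhage endpoints are listed separately, as safety outcomes, in section 8.1.3.

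Section 18.3 says of the 24-hour NCCT: "The NCCT study should include the whole head". The 24-hour CTA runs from the aortic arch to the vertex, and all series go to the core lab. Section 19 adds that, across the trial consortium, "there is an independent outcome assessment committee, imaging assessment committee and adverse event committee".

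**The concern.** A reason that holds for some endpoints is used to drop blinding for all of them. Treatment is open label, so anyone who judges an endpoint with knowledge of the allocation can be influenced by it.

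The protocol records expectations that could act in this way. It names a lower risk of recurrent stroke as a benefit of immediate stenting (Summary, section 6.4), and it foresees a comparable to slightly higher risk of intracranial haemorrhage (section 13.2). Whether a transient deficit counts as a TIA, or a deterioration as a new stroke, is a matter of judgement. Recurrent stroke is also one of the three items named in the secondary objective (section 2).

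This is not a detail that can wait for the analysis plan. Who sees the allocation when an endpoint is assessed is settled during conduct, and no analysis restores blinding afterwards.

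**Working it through.** The plan gives no figure on this point, so no arithmetic applies. The check sets the rule in 8.2 against each endpoint and asks whether the stated reason, that stenting is obvious to the assessor, holds.

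**Secondary endpoints (8.1.2)**

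- *mRS 0-1, 0-2 and 0-3.* The reason does not hold. These are cut-points of the 90-day mRS, which 8.1.1 and 8.2 say is scored blind. Read literally, two adjacent sentences of 8.2 give the same score opposite blinding status.
- *Mortality.* Objective; blinding matters little.
- *EQ-5D-5L.* Self-completed (sections 17.1 to 17.3) by a patient who knows the treatment, so a blinded rater changes nothing.
- *Final infarct volume.* The reason does not hold. It is read on a head scan, and the stent lies in the neck.
- *Any stroke; recurrent ipsilateral TIA or ischaemic stroke.* The reason does not hold for adjudication. Records can be redacted for allocation, although details of later carotid treatment or antiplatelet drugs may still give it away.
- *Carotid re-occlusion at 24 hours and 90 days.* The reason holds: cervical CTA and duplex show the stent.
- *TICI and AOL.* The reason holds unless the images are cropped. Section 18.2 requires runs of the carotid bifurcation, and the 24-hour CTA includes the neck.
- *NIHSS at 24 hours and day 5-7.* A bedside score. A core lab or committee cannot produce it, so it can be blinded only by a masked rater.

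**Safety outcomes (8.1.3)**

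- *Symptomatic intracerebral haemorrhage.* The sentence in 8.2 does not name it, and its blinding is not stated in 8.1.3 or 8.2.
- *Asymptomatic haemorrhage and subarachnoid haemorrhage at day 1.* Blinding is likewise not stated. Both are read on brain CT, so masked reading is possible.
- *Bradycardia or hypotension during CAS.* The definition itself reveals the allocation.

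**Design statements.** The Summary and section 3 do not limit blinded outcome assessment to the primary endpoint, whereas 8.2 does so for most purposes. A reader of the Summary would expect more blinding than 8.2 provides.

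**Feasibility.** Section 12.1 has pseudonymised images sent to the core lab or the sponsor, section 18.3 sends all 24-hour series to the core lab, and section 19 provides independent committees. The structure for masked reading and adjudication is largely in place. What is missing is a statement that it is used masked.

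**The case against.** The strongest defence is that 8.2 discloses the exception openly, that the more specific section governs, and that the endpoint carrying the conclusion is blinded. Much of this stands. Three stronger readings are tempting, and the documents do not support them.

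- *That the trial is not a PROBE trial.* The mRS and the 90-day follow-up are assessed blind, so the label can stand for the primary endpoint. The conflict is only with unqualified wording in the Summary and section 3.
- *That symptomatic intracerebral haemorrhage is declared unblinded, or that blinded committees exist and are bypassed.* The sentence concerns secondary endpoints, and this haemorrhage endpoint is a safety outcome whose blinding is unstated. Section 19 calls the committees independent and does not call them blinded.
- *That the bias can be sized.* One could apply the 5-10% risk in section 12.2 to 300 patients per arm, giving 300 × 0.05 = 15 to 300 × 0.10 = 30 events per arm, and suppose that some are misclassified. Any such number of misclassified events would be invented, and the protocol sets no safety margin to compare it with; its only margin is the common odds ratio of 0.8 on the mRS. That risk figure also concerns haemorrhage, which the sentence does not cover.

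It is also fair to object that not everything can be masked. Bedside NIHSS, events defined by the stenting procedure, and carotid patency cannot be handed to a masked core lab. A demand to blind all secondary and safety endpoints would fail. Redaction takes real work and may be incomplete.

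What remains is narrower: for infarct volume and for stroke and TIA adjudication, the stated reason does not apply and masking is practicable.

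**Conclusion.** The point holds in a limited form. Section 8.2 applies a reason valid for some secondary endpoints to the whole list. The reason fails for final infarct volume on the 24-hour head NCCT and for adjudication of any stroke and recurrent ipsilateral TIA or ischaemic stroke. Taken literally, the rule also contradicts the blinded mRS behind three secondary endpoints and the unqualified wording of the Summary and section 3. For symptomatic intracerebral haemorrhage the finding is only that the protocol does not say whether adjudication is blinded.

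The consequence is an avoidable risk of detection bias in secondary and, possibly, safety comparisons. No numerical size is claimed. The primary non-inferiority analysis is unaffected. The conclusion assumes that the head NCCT does not show the cervical stent and that event records can be redacted well enough to hide allocation in most cases.

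**What to change.** Replace the general sentence in 8.2 with an endpoint-by-endpoint statement:

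- The existing imaging core lab reads final infarct volume, and intracerebral and subarachnoid haemorrhage on the 24-hour head NCCT, blinded to allocation.
- The existing independent committees adjudicate any stroke and recurrent ipsilateral TIA or ischaemic stroke from records redacted for allocation. Symptomatic intracerebral haemorrhage is adjudicated in the same way. Name the committee responsible for each.
- The mRS dichotomies are stated to come from the blinded 90-day mRS.
- Only endpoints where allocation is unavoidably known are listed as unblinded: carotid re-occlusion on cervical CTA or duplex, bradycardia or hypotension during CAS, bedside NIHSS unless a masked rater is already available, and TICI and AOL unless the cervical segment is cropped.

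Qualify the blinded-outcome statements in the Summary and section 3 to match.

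The cost is a wording change plus masking in the core lab and redaction of event records. No additional scans are needed, because the 24-hour images already go to the core lab. Some unmasking may remain through treatment details in the records, and the protocol should say so.

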### **8.3 Study procedures**

All patients receive a non-contrast brain CT, perfusion CT and CT-angiography at baseline (as part of usual patient care) and at 24 hours a non-contrast brain CT and CT-angiography (for research purpose).. At 90 days a duplex ultrasound of the ICA is performed.

### **8.4 Withdrawal of individual subjects**

Subjects can leave the study at any time for any reason if they wish to do so without any consequences. The investigator can decide to withdraw a subject from the study for urgent medical reasons. Data from patients who waive consent will not be used for the primary endpoint of the study, but their data will be used in a strictly anonymized form to obtain data for the purpose of safety analysis to accurately describe the group without consent.

#### **8.4.1 Specific criteria for withdrawal (if applicable)**

n/a

### **8.5 Replacement of individual subjects after withdrawal**

For every patient without consent, an additional patient will be included.

### **8.6 Follow-up of subjects withdrawn from treatment**

Due to the deferred consent procedure, the patients are already allocated to the intervention or control group, before informed consent from the patient or their legal representative has been obtained. In order to monitor the safety of the intervention and control group, we will explicitly communicate to the patients or legal representatives who do not consent, that we will anonymously register at least SAE's, (symptomatic) intracerebral hemorrhage and mortality.

### **8.7 Premature termination of the study**

The study will be terminated prematurely in case the DSMB advises to stop patient recruitment. The database will be closed after 90 days assessment and the trial results will be reported.

### 9.1 Temporary halt for reasons of subject safety

In accordance to section 10, subsection 4, of the WMO, and applicable local regulations of the participating countries, the sponsor will suspend the study if there is sufficient ground that continuation of the study will jeopardise subject health or safety. The sponsor will notify the accredited METC without undue delay of a temporary halt including the reason for such an action. The study will be suspended pending a further positive decision by the accredited METC. The investigator will take care that all subjects are kept informed.

### 9.2 AEs, SAEs and SUSARs

#### 9.2.1 Adverse events (AEs)

Adverse events are defined as any undesirable experience occurring to a subject during the study, whether or not considered related to trial procedure. All adverse events reported spontaneously by the subject or observed by the investigator or his staff will be recorded.

#### 9.2.2 Serious adverse events (SAEs)

A serious adverse event is any untoward medical occurrence or effect that

- results in death;
- is life threatening (at the time of the event);
- requires hospitalization or prolongation of existing inpatients' hospitalisation;
- results in persistent or significant disability or incapacity;
- is a congenital anomaly or birth defect; (not relevant for CASES) or
- any other important medical event that did not result in any of the outcomes listed above due to medical or surgical intervention but could have been based upon appropriate judgement by the investigator.

An elective hospital admission will not be considered as a serious adverse event.

The investigator will report all SAEs to the sponsor without undue delay (< 24 hours) after obtaining knowledge of the events.

The sponsor will report the SAEs through the web portal to the accredited METC that approved the protocol, within 7 days of first knowledge for SAEs that result in death or are life threatening followed by a period of maximum of 8 days to complete the initial preliminary report. All other SAEs will be reported within a period of maximum 15 days after the sponsor has first knowledge of the serious adverse events.

#### 9.2.3 Suspected unexpected serious adverse reactions (SUSARs)

N/A

### **9.3 Annual safety report**

In addition to the expedited reporting of SUSARs, the sponsor will submit, once a year throughout the clinical trial, a safety report to the accredited METC, competent authority, and competent authorities of the concerned Member States.

This safety report consists of:

- a list of all suspected (unexpected or expected) serious adverse reactions, along with an aggregated summary table of all reported serious adverse reactions, ordered by organ system, per study;
- a report concerning the safety of the subjects, consisting of a complete safety analysis and an evaluation of the balance between the efficacy and the harmfulness of the medicine under investigation.

### **9.4 Follow-up of adverse events**

All AEs will be followed until they have abated, or until a stable situation has been reached. Depending on the event, follow up may require additional tests or medical procedures as indicated, and/or referral to the general physician or a medical specialist. SAEs need to be reported till end of study within the Netherlands, as defined in the protocol

### **9.5 Data Safety Monitoring Board (DSMB) / Safety Committee**

The trial will be monitored by a DSMB, that will include a vascular neurologist, neuro-interventionist and an independent methodologist/statistician. The role of the DSMB is to monitor the safety of the trial and to provide the steering committee with recommendations on the continuation or termination of the trial.

The objectives of the DSMB are:

- To monitor the safety data of the included patients
- To analyze efficacy data in both arms of the trial
- To evaluate the overall conduct of the trial, protocol violations, compliance to previous DSMB recommendations, recruitment rates, losses to follow up, and trial monitoring

The DSMB will meet once before the first inclusion and thereafter twice a year during the patient recruitment phase. An efficacy interim analysis will be performed after 300 included patients have reached their 90 day follow-up. For the efficacy interim analysis, the DSMB will analyze the distribution of mRS scores at 90 days in both arms. The Haybittle-Peto boundary rule for premature termination of the trial will be applied.

For the safety interim analyses, the DSMB will evaluate the mortality, the incidence of symptomatic intracranial hemorrhage and other endpoints concerning SAE's. Safety assessments are required after every 5 symptomatic intracranial hemorrhages and after every 10 deaths. In the light of these analyses, the DSMB will advise the chairman of the Steering committee if, in their view, the randomized comparisons in the trial have provided both (i) "proof beyond reasonable doubt" that for all, or for some specific types of patients, one particular treatment is clearly indicated or clearly contraindicated in terms of a net

difference in outcome, and (ii) evidence that might reasonably be expected to influence materially patient management. Appropriate criteria of proof beyond reasonable doubt cannot be specified precisely, but a difference of at least 3 standard deviations in an interim analysis of a safety endpoint may be needed to justify halting, or modifying, the study prematurely. This criterion has the practical advantage that the number of interim analyses is of little importance.

The advice(s) of the DSMB will only be sent to the sponsor of the study by the chair of the trial steering committee. Should the steering committee decide not to fully implement the advice of the DSMB, the sponsor will send the advice to the reviewing METC, including a note to substantiate why (part of) the advice of the DSMB will not be followed.

## **10. STATISTICAL ANALYSIS**

The statistical analysis and reporting of the trial will be in accordance with the CONSORT guidelines. Baseline data will be reported by treatment allocation as categorical or continuous variables, where appropriate. Missing baseline data will be imputed using regression imputation. For the primary endpoint, statistical analyses will be performed according to the per-protocol (PP) principle as well as the intention to treat (ITT) principle. Both PP and ITT analyses must demonstrate non-inferiority in order to conclude that immediate CAS during EVT is non-inferior to a deferred treatment strategy.

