For the sample size calculation, we used data from the Dutch MR CLEAN registry, a nationwide cohort of EVT treated patients between 2014-2018. Based on the mRS distributions in the immediate CAS group (mRS 0: 17.9%, mRS 1: 22.3%, mRS 2: 16.7%, mRS 3: 14.4%, mRS 4: 12.3%, mRS 5: 5.0%, mRS 6: 11.4%) and in the deferred treatment group (mRS 0: 6.9%, mRS 1: 20.2%, mRS 2: 17.9%, mRS 3: 16.4%, mRS 4: 17.2%, mRS 5: 8.0%, mRS 6: 13.4%), we calculated the assumed effect size to be a common odds ratio (cOR) of 1.15 for a shift in favorable direction on the full mRS. The non-inferiority margin was set to a cOR of 0.8, corresponding to an absolute difference of approximately 5% in favorable outcome (mRS 0-2). This is a generally accepted margin in the stroke research community and has been recently used in comparable EVT trials. We used Monte Carlo simulations with 5000 runs to calculate the required sample size based on the assumptions above showing that a sample size of 610 patients, would provide 80% power (at a two-sided alpha level of 0.05) to determine that the lower bound of the cOR 95% confidence interval (CI) does not cross the non-inferiority margin of 0.8. Covariate adjustment for major prognostic variables that included age, pre-stroke mRS score, stroke severity, collateral score and time from symptom onset to randomization results in a reduction of at least 15% in the required sample size (n=520). Assuming a crossover rate of 3% in each arm (6% for both groups), necessitates an increase in sample size by factor  $1/(1 - \% \text{ crossover})^2 = 1/(1 - 0.06)^2 = 1.13$ . So taking crossovers into account, the sample size increases to 588 (520\*1.13). Based on the experience of the MR CLEAN NO-IV trial and MR CLEAN-MED trial, the number of patients lost to follow up is expected to be low

(0 in both recently completed trials). Assuming a combined percentage of 2% due to loss to follow up and to erroneous inclusions (for example inclusion of patients who appear to have carotid dissection or carotid pseudo-occlusion) the sample size will need to be increased to a total sample size of 600 patients (n= 300 per group).

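### The 80% power in section 4.5 is for one confidence-interval test, while section 10 requires both ITT and PP to succeed, so the power of the trial's actual decision rule is not stated

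*Protocol*

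**What the plan says.** Section 4.5 of the protocol describes a Monte Carlo calculation that arrives at 610 patients, a number that "would provide 80% power (at a two-sided alpha level of 0.05"). Success there means that a single cOR has its lower 95% limit above the margin. The planning values are explicit: "we calculated the assumed effect size to be a common odds ratio (cOR) of 1.15", and "The non-inferiority margin was set to a cOR of 0.8". Covariate adjustment "results in a reduction of at least 15% in the required sample size (n=520"). The number then rises to 588 for crossover (3% per arm, factor 1.13) and to 600 for 2% loss to follow-up and erroneous inclusions.

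Section 10 fixes how the trial is judged: "Both PP and ITT analyses must demonstrate non-inferiority in order to conclude that immediate CAS during EVT is non-inferior". Section 10.1 defines the PP set by the absence of major protocol violations, settled at a review blinded to outcome. It gives no expected share of patients to be excluded.

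**The concern.** The power statement concerns one event, and the conclusion depends on two. ITT and PP results are strongly correlated because they share most patients, but the correlation is not perfect. Joint success is therefore less likely than success in the weaker of the two analyses. None of the steps 610, 520, 588 and 600 refers to the joint rule.

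This does not wait for the SAP, because the protocol itself prints the power figure and fixes the rule, and the two do not describe the same event. If non-inferiority is not concluded, the DSMB, the funders and readers will judge that result against a power that was never calculated for the rule in use.

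**Working it through.** **1. The printed figure.** Inputs from section 4.5: cOR 1.15, margin 0.8, two-sided 0.05, and the deferred-group mRS distribution (6.9, 20.2, 17.9, 16.4, 17.2, 8.0 and 13.4% for scores 0 to 6).

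- Distance to the margin: ln(1.15/0.8) = 0.3629, squared 0.1317.
- Shifting the deferred distribution by 1.15 and averaging the arms gives 1 − Σp̄³ = 0.9727.
- Whitehead's proportional-odds formula: N = 12(1.960 + 0.842)² / (0.1317 × 0.9727) ≈ 735.
- At N = 610: 0.3629 × √(610 × 0.9727/12) = 2.552, and Φ(2.552 − 1.960) = 72.3%. A 4,000-run simulation gave 72.4%.
- With a one-sided 5% bound the formula gives 81.8% at 610, but section 4.5 does not state that bound.

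So 80% at 610 does not reproduce from the stated inputs. The later steps do: 610 × 0.85 = 518.5 (printed 520), 520 × 1.13 ≈ 588, 588/0.98 = 600.

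**2. Joint power, accepting that 520 adjusted patients give 80%.** The ITT and PP z-statistics are treated as bivariate normal with correlation √s, where s is the share of patients kept in PP. The share is an assumption: 6% excluded, range 2–10%. For scale, 3% crossover per arm is 9 + 9 = 18 of 600 patients, or 3%, and the 2% step could bring this to about 5%.

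(a) *Both analyses set at exactly 80%, inflation ignored.* Joint power is 78.4% at 2% excluded, 77.2% at 6% and 76.4% at 10%. At 6% the loss is 2.8 points.

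(b) *Inflation to 588 kept, with the dilution convention behind the 1.13 factor (the whole distance to the margin shrinks by 6%).*
- ITT mean: 2.802 × √(588/520) × 0.94 = 2.800, power 80.0%.
- PP mean (crossovers removed, 6% fewer patients): 2.802 × 1.0634 × √0.94 = 2.888, power 82.3%.
- Joint: 78.3%, which is 1.7 points below ITT and below the printed 80%.

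(c) *Inflation kept, crossover diluting only ln(1.15) and not the distance from 1 to 0.8.*
- Dilution factor: (0.94 × 0.1398 + 0.2231)/0.3629 = 0.977.
- ITT mean: 2.802 × 1.0634 × 0.977 = 2.910, power 82.9%. PP is 82.3% as in (b).
- Joint: 80.1%, which is 2.8 points below ITT, with no shortfall against 80%.

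At 10% excluded, (b) and (c) give 76.8% and 78.3%, so shortfalls of 3.2 and 1.7 points. At 2% excluded, with PP mean 2.802 × 1.0634 × √0.98 = 2.949, they give 79.7% and 81.9%.

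An unadjusted 4,000-run simulation removed crossovers of 3% or 5% per arm from PP. Joint success was about 1.4 to 2 points below ITT (for example ITT 77.0%, PP 77.8%, both 75.3% at N = 736 with 3% per arm).

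**3. Joint power from the stated inputs, not accepting 520 as 80%.** With 588 evaluable patients and the 15% covariate gain, √(588 × 0.9727/(12 × 0.85)) = 7.488.
- ITT: (0.94 × 0.1398 + 0.2231) × 7.488 = 2.655, power about 76%.
- PP, 6% excluded: 0.3629 × 7.488 × √0.94 = 2.635, power about 75%.
- Joint: about 72%, and about 70% at 10% excluded.

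**The case against.** Section 4.5 says exactly what its 80% covers and does not call it joint power. The steps to 588 and 600 add patients for crossovers and erroneous inclusions, much the same patients a PP analysis might drop. Removing 6% of 588 leaves about 553, still above 520, so on the protocol's own premise PP power exceeds 80%. The PP set is also not defined as dropping all crossovers: section 10.1 excludes major violations, and section 5.1 allows crossovers with a valid reason not to count as violations. Fewer exclusions mean a higher correlation and a smaller loss.

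All of this stands as a limit on the size. A reader might infer that the trial's power is about 3 points lower than stated. The documents do not support a fixed figure of that kind:

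- The 2.8 points at 6% need both analyses at exactly 80%, which ignores the inflation. With the inflation kept, 3 points needs roughly 10% excluded under the convention in (b).
- A simulation at N = 600 with 3% crossover per arm and 2% erroneous inclusions gives 79.8% for ITT and 77.0% for both. It uses an unadjusted model and a one-sided 5% bound, neither of which is the protocol's specification. With the 95% interval the same unadjusted simulation gives 68.5% and 65.9%.

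The objection does not remove the mismatch. The inflation was added for crossover, loss and erroneous inclusion, and section 4.5 does not show that it also covers a two-analysis rule.

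**Conclusion.** The point holds as a mismatch between the power statement and the decision rule. The 80% describes one analysis, and the power of requiring both is not stated.

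Taking 520 adjusted patients as 80% and assuming 6% PP exclusion, joint power is about 1.7 to 2.8 points below ITT power. Against the printed 80%, the shortfall is about 0 to 1.7 points with the inflation counted, and 0 to about 3 points over 2–10% excluded. These figures rest on the normal approximation, the √s correlation, PP being free of crossover dilution, and an exclusion rate the protocol does not give.

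The larger difficulty is separate: with the stated 95% interval, single-analysis power at 610 is about 72%, and joint power with 588 evaluable patients and the covariate gain is about 70–72%. That gap comes mostly from the baseline and should not be attributed to the two-analysis rule.

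**What to change.** In section 4.5, rerun the Monte Carlo calculation with the stated 95% confidence interval, the adjusted model, the crossover and erroneous-inclusion assumptions, and a stated PP exclusion rate with a range (for example 2–10%). Build the ITT and PP sets in every run and report the proportion of runs in which both lower limits exceed 0.8 as the power of the trial. ITT and PP power may be given beside it, labelled as single-analysis figures. Keep N = 600, and do not print a fixed deduction such as 3 points.

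The cost is one rerun of an existing simulation and a revised power sentence. No patients are added, and the margin, analysis and decision rule are unchanged. The printed power will probably be less favourable, mainly because of the baseline.
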